# 9.1.2 Adverse Events Collection and Reporting

All AEs and SAEs, whether related or not related to study drug, including those thought to be associated with protocol-specified procedures, must be collected throughout the study from the time of patient signing the consent form until the end of study visit, or until the patient's last study visit. All reported AEs and SAEs will be followed until resolution. The Investigator should take appropriate measures to follow all AEs until clinical recovery is complete and laboratory results have returned to normal, or until progression has been stabilized, or until death, in order to ensure the safety of the patients. This may imply that observations will continue beyond the last planned visit per protocol, and that additional investigations may be requested by the monitoring team up to as noticed by the Sponsor. When treatment is prematurely discontinued, the patient's observations will continue until the end of the study as defined by the protocol for that patient.

All AEs will be recorded on the eCRFs. The records will describe the nature (diagnosis or single syndrome as much as possible, alternatively signs and symptoms) severity, using the NCI CTCAE term (version 4.3 of June 14, 2010), date/time of onset, date/time of end, actions taken with respect to IMP, corrective treatment/therapy given, additional investigations performed, outcome, and causality (relationship to study treatment according to the investigator's assessment).

It will be specified whether the event is serious or not according to the definition of SAE (See section 9.1.1).

A sponsor safety representative will determine the causal relationship when it is not clearly provided by the investigator.

Laboratory, vital signs or ECG abnormalities are to be recorded as AEs only if:

- o Symptomatic and/or
- Requiring either corrective treatment or consultation, and/or
- Leading to IMP discontinuation or modification of dosing, and/or
- Fulfilling a seriousness criterion

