#### 9.1.4 Abnormal laboratory values/vital signs

The reporting of laboratory / vital signs / ECG abnormalities as laboratory findings / vital signs / ECG and as AEs should be avoided. They should not be reported as AEs (using the NCI CTCAE version 4.3 of June 14, 2010 terminology) unless any one of the following are met:

- o Any criterion for a SAE is fulfilled
- The laboratory / vital signs / ECG abnormality causes the subject to discontinue from the study treatment

Release date: Edition number

MOD-3783

12 August 2016

GED version

- The laboratory / vital signs / ECG abnormality causes the subject to interrupt the study treatment
- The laboratory / vital signs / ECG abnormality requires intervention as corrective treatment or consultation and/or
- Symptomatic and/or
- o The Investigator believes that the abnormality should be reported as an AE

All laboratory tests for which abnormal results are collected after the initiation of study treatment should be repeated until the values return to normal or to a stable status. Abnormal results are defined as those falling out of the normal laboratory range and that are clinically significant. The frequency with which such checks should be made will be defined by the investigator's opinion depending on the degree of abnormality.

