#### CONFIDENTIAL

Release date: Edition number

MOD-3783

12 August 2016

GED version

Body weight should be obtained at screening visit and at end of treatment, with the patient wearing undergarments or very light clothing and no shoes, and with an empty bladder. The floor surface on which the scale rests must be hard and should not be carpeted or covered with other soft material. The same scale should be used throughout the study, and calibrated on a regular basis as recommended by the manufacturer. The weight is read and recorded in the e-CRF and Source Data. Self-reported weights are not

- o Collection of AEs
- o 12 lead ECG standard. The ECG machine should compute the heart rate, PR, QT and QTC (calculated using Bazett's formula), QRS duration. The investigator or a cardiologist will evaluate the ECG. ECGs which are assessed by them as "abnormal, clinically significant", should be reported as AEs. A standard copy of each anonymized ECG should be archived by the sponsor of the study

acceptable and patients must not read the scales themselves

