9.6 Vital Signs, Physical Findings and Other Observations Related to Safety

[figure not shown]
Descriptive statistics of ECOG results will be presented by a shift table, comparing the worst value over the study versus baseline.

Descriptive statistics of ECGs results (normal, abnormal not clinically significant, abnormal clinically significant), heart rate, PR interval, QT interval, Bazzett's QTc and QRS duration will be presented by visit. For the continuous parameters, both absolute values and change from baseline will be presented. Unscheduled visits will not be taken into account.

Data from vital signs and physical examination will only be listed.

10. References

- [2] Fleming T. One sample multiple testing procedure for phase II clinical trials. Biometrics 1982;38:143-151.
- [3] Common Terminology Criteria for Adverse Events (CTCAE) Version 4.03, dd. June 14, 2010 National Cancer Institute

TPL N°: eTPL SA-02-01 TPL Version: 02 Of SOP SA-02.08

TPL N°: eTPL SA-02-01 TPL Version: 02

Of SOP SA-02.08
TPL Effective Date: 31 Mar 2016
Approved in Vault: 3/8/2019

[figure not shown]
Confidential	

TPL N°: eTPL SA-02-01 Of SOP SA-02.08 TPL Effective Date: 31 Mar 2016 TPL Version: 02

Approved in Vault: 3/8/2019

Innate - IPH2201-202

Version: 2.0

Page 26 of 26

TPL N°: eTPL SA-02-01 Of SOP SA-02.08 TPL Effective Date: 31 Mar 2016 TPL Version: 02

Approved in Vault: 3/8/2019

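### Protocol 9.1.2, 9.1.4 and 9.2.1 give different rules for when an ECG finding is an AE, and SAP 9.6 ignores unscheduled visits, so a clinically significant ECG from an unscheduled visit could reach no AE or ECG table

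*Protocol*

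**What the plan says.** Three protocol sections decide whether an ECG finding becomes an adverse event.

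- **Section 9.2.1 (Clinical Safety).** The investigator or a cardiologist reads the ECG. Those classed as abnormal and clinically significant "should be reported as AEs". No further condition is attached.
- **Section 9.1.2 (Adverse Events Collection and Reporting).** "Laboratory, vital signs or ECG abnormalities are to be recorded as AEs only if" one of four grounds applies: the abnormality is symptomatic; "Requiring either corrective treatment or consultation, and/or"; "Leading to IMP discontinuation or modification of dosing, and/or"; "Fulfilling a seriousness criterion". Clinical significance is not a ground.
- **Section 9.1.4 (Abnormal laboratory values/vital signs).** This section discourages reporting such abnormalities as AEs unless one of six conditions is met. The last is: "The Investigator believes that the abnormality should be reported as an AE".

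On the analysis side, SAP 9.6 presents the ECG interpretation (including the clinically significant category), heart rate and the PR, QT, QTc and QRS values by visit. It adds: "Unscheduled visits will not be taken into account". SAP 9.3 tabulates recorded treatment-emergent AEs. SAP 4.1 promises individual listings for whatever the tables present.

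The flow-chart footnotes for both phases plan ECGs at screening, W0 (pre-dose and about three hours after the start of infusion), W6, W16, W32 and EOS.

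**The concern.** For a clinically significant ECG that meets none of the four grounds in 9.1.2, a site cannot obey both 9.2.1 and 9.1.2. One site records an AE and another does not, from the same tracing. Occurrence of AEs and SAEs is a phase Ib primary endpoint (protocol 3.1.1), and protocol 3.1.1 and 3.1.2 name ECG results as part of the safety evaluation in phase Ib and phase IIa respectively.

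Normally the ECG summary would be a second route into the report, so that inconsistent AE recording would not hide the finding. Here the summary disregards unscheduled visits. For a tracing from such a visit, AE recording is the only tabulated route the plan provides, and that is the route on which the protocol disagrees with itself.

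**Working it through.** No sample size, power or event count is involved. The check has two parts: follow such a tracing through the rules, then measure how long patients go without a planned ECG.

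**1. Where does the tracing end up?** Take an ECG read as clinically significant that has no symptoms, no corrective treatment or consultation, no IMP discontinuation or dosing change, and no seriousness criterion.

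| Taken at | Rule the site follows | AE recorded | SAP 9.3 AE tables | SAP 9.6 ECG summary |
|---|---|---|---|---|
| Visit with a planned ECG | any | depends on the rule | only if an AE is recorded | yes |
| Unscheduled visit | 9.2.1 | yes | yes, if treatment-emergent | no |
| Unscheduled visit | 9.1.4 | investigator decides | only if an AE is recorded | no |
| Unscheduled visit | 9.1.2 | no | no | no |
| Planned visit with no planned ECG | any | depends on the rule | only if an AE is recorded | not stated |

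Only the fourth row is a complete omission from the tables. In all three unscheduled-visit rows the measured intervals, QTc among them, enter no numerical summary, even where an AE is recorded.

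**2. Is there a listing to fall back on?** SAP 4.1 assures listings for tabulated data. It does not restrict listings to those data: SAP 9.6 itself lists vital signs and physical examination without tabulating them. So a listing of ECGs from unscheduled visits is neither promised nor ruled out.

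**3. How long is the interval without a planned ECG?** Inputs: last on-treatment ECG at W32; EOT at W56 (phase Ib) or W52 (phase IIa); EOS at 12 months plus one week after EOT (visit correlation tables). With 12 months taken as 52 weeks:

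- Phase IIa: EOS = 52 + 52 + 1 = W105; interval = 105 − 32 = 73 weeks, of which 105 − 52 = 53 follow EOT and 73 − 53 = 20 precede it.
- Phase Ib: EOS = 56 + 52 + 1 = W109; interval = 109 − 32 = 77 weeks, of which 109 − 56 = 53 follow EOT and 77 − 53 = 24 precede it.

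Ibrutinib is planned through follow-up in both phases (protocol 3.4), so most of the interval is still on study treatment. These figures apply to patients who complete. EOS, with its ECG, is also performed on premature discontinuation, so patients who stop early have a planned ECG sooner.

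**4. Are ECGs outside the schedule foreseen?** Yes. Protocol 3.3.4 mentions one on evidence of tumor lysis syndrome. That example would often be accompanied by symptoms or treatment, and so qualify under 9.1.2 anyway. It shows that off-schedule tracings occur, not that they would be lost.

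**The case against.** The strongest reply is that existing text nearly reconciles the rules. Section 9.2.1 is specific to ECGs, and 9.1.4 lets an investigator report any abnormality he or she thinks should be an AE. An investigator who calls a tracing clinically significant can report it under both. An omission requires a site to apply 9.1.2 alone. That is fair, but 9.1.2 is the general AE collection section, its wording is exclusive, and 9.1.4 permits reporting without requiring it. The inconsistency stands.

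The second reply is that the affected case is narrow. ECGs prompted by a clinical concern will often be symptomatic or lead to consultation or treatment. A grade 3 or higher AE suspends IPH2201 under protocol 3.3.1, which would meet the dosing ground. This stands: the gap mainly concerns lower-grade findings.

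The third reply is that by-visit tables on scheduled visits are a legitimate choice in a small descriptive trial. They are, and nothing here asks for their removal. But the same SAP section already compares the worst ECOG value over the study with baseline, so a worst-value summary for ECGs uses a method the plan has adopted.

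A reader might also infer more than the documents support:

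- That any asymptomatic significant ECG can vanish. Scheduled ones stay in the SAP 9.6 table, and absence of symptoms alone does not take a finding outside 9.1.2.
- That every ECG between W32 and EOS is excluded. SAP 9.6 excludes unscheduled visits. An ECG added at a planned visit, such as W40, EOT or a follow-up visit, is not clearly excluded.
- That SAP 4.1 prevents a listing. It guarantees some listings and is silent on others.

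**Conclusion.** The point holds in a limited form. Three protocol sections give inconsistent rules for turning an ECG finding into an AE, so a component of a phase Ib primary endpoint can be recorded differently between sites. In addition, a clinically significant ECG from an unscheduled visit that meets none of the four grounds in 9.1.2 could appear in no AE or ECG table, and QTc values from unscheduled visits enter no summary at all.

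The number of such tracings cannot be derived from the documents. The 73 weeks (phase IIa) and 77 weeks (phase Ib) describe how long a completing patient has no planned ECG; they do not measure how much is lost. It would be tempting to conclude that the ECG summaries will lean toward normal tracings. They could, but nothing in the documents shows that they would.

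The conclusion assumes that some sites apply 9.1.2 as written and that some ECGs are taken at unscheduled visits. The available SAP text passes from 9.4 to 9.6, and nothing is inferred from that.

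**What to change.** **Protocol.** Reconcile 9.1.2, 9.1.4 and 9.2.1 into one ECG-to-AE rule. One way is to add an ECG assessed as abnormal and clinically significant to the lists in 9.1.2 and 9.1.4, so that both agree with 9.2.1.

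**SAP 9.6.** Keep the by-visit table. Add, per patient, the worst post-baseline ECG interpretation against baseline and the maximum post-baseline QTc, with a listing, all including unscheduled ECGs. State whether an ECG added at a planned visit without a planned ECG counts in the by-visit table.

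**Cost.** One line in two protocol lists, and one extra table and listing in the SAP. No new ECG is needed. The AE count may rise slightly. If the protocol can no longer be amended, the SAP additions still bring the recorded ECGs into the report, but they do not make AE recording consistent between sites; the study report should then state that limitation.

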# 9.2.2 Laboratory Investigations

The primary endpoint will be The safety of 2 repeated administrations of IPH2201 given as a single agent during 4 weeks during 2 cycles of 14 days, and thereafter, given in combination with ibrutinib during 26 14 cycles 52 weeks is the primary endpoint during the dose escalation part of the trial.

- Occurrence of DLT and identification, if any, of the MTD, during the administration of IPH2201 as a single agent and given in combination with ibrutinib
- Occurrence of AEs and SAEs

Safety will be assessed using the CTCAE version 4.03; it will include a descriptive analysis of the frequency and severity of AEs; related AEs followed to resolution (≤ grade 1) unless deemed irreversible and clinical laboratory tests collected to assess lab abnormalities, as well as results of vital sign measurements, electrocardiograms (ECGs), physical examinations and imaging studies.

The following laboratory blood tests will be performed at study site according to the study flow chart:

- Hematology: RBC, WBC with differential count, platelets, hemoglobin, MCV hematocrit
   Serum Biochemistry: sodium, potassium, calcium, magnesium, total proteins, and albumin, urea, uric acid, creatinine, calculated creatinine clearance, ALP, total bilirubin, LDH, lipase, amylase, AST (SGOT), ALT (SGPT), GGT, glucose, CRP and fibrinogen
- o Coagulation factors: APTT
- o prothrombin time (PT)
- o Serology HIV HCV HPV

Other tests will also be performed: urinary pregnancy test, and urinalysis (PH, glucose, leucocytes, proteins, blood and hemoglobin).

Abnormal laboratory values considered to be clinically relevant by the investigator must be repeated to rule out laboratory error and followed up until they have returned to normal except if an adequate explanation is found.

Release date: Edition number

GED version

#### 9.3 SAFETY COMMITTEE

A safety committee will be constituted to monitor data and overall safety in this study in order to determine the dose to be administered to the patients after phase lb.

The safety committee will consist of:

- The principal investigators of the study
- A sponsor medical and pharmacologist representative
- The sub-investigators as optional members, including the Director of the division of Hematology at OSU as hematologist with high experience in CLL
- A methodologist or physicians with relevant expertise related to the reviewed safety issues can
  join the safety committee as optional member

The Safety Committee will review the data for progression and safety with data collected as following:

- During the dose escalation phase Ib of the trial, at each dose level after the completion of the 2 cycles of IPH2201 by the *last* patient of the cohort
- o During phase Ib, at each dose level the safety committee will also review patients data after completion of 2 cycles of IPH2201 in combination with ibrutinib by the *last* patient of the cohort
- o Furthermore, at any time during the phase lb, considering any additional safety information, the safety committee may decide to decrease the dose of IPH2201 to a lower dose level
- During the phase IIa of the trial, every six months
- The Safety Committee could also be involved at any time should a major safety issue occur.

The functions of the safety committee are multiple:

- To analyze the causality of the AEs in phase Ib
- At each dose level, to allow dose escalation as above described
- To select the dose of IPH2201 which will be assessed during the phase IIa, taking into account all the safety, pharmacology and anti-leukemia activity data gathered at each dose level, with a minimum of follow-up of 4 weeks after the introduction of ibrutinib, in the last patient enrolled in the dose escalation study. Such a dose may correspond to the MTD, to the highest tested dose level or to a lower dose level, chosen during or at the end of the dose escalation. The safety committee may therefore decide to stop prematurely the dose escalation, even if the MTD was not reached. The report of the safety committee will be forwarded to the FDA
- To recommend the discontinuation of the study, transiently or permanently, or a decrease in the dose, after the occurrence of 2 unacceptable reactions in patients treated by the combination of IPH2201 and ibrutinib during the first or second phase of the study

DLTs and unacceptable reactions are defined as:

- Any grade 3 or grade 4 non hematologic toxicity
- o Grade 4 neutropenia (ANC < 500/μI) lasting ≥7 days after discontinuation of therapy in patients with pre-treatment ANC ≥ 1,000/μI
- o Grade 4 thrombocytopenia (platelet count <20,000/μl and/or ≥75% decrease from pre-treatment value)
- Grade 3 or 4 thrombocytopenia associated with bleeding
- Any dose delay due to AE for > 14 consecutive days

Such events will be considered as DLTs whenever they occurred during the first 4 cycles (8 weeks) of treatment in phase Ib (including 2 administrations of treatment with IPH2201 alone and 2 administrations of treatment with IPH2201 + ibrutinib).

Release date: Edition number

GED version

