### Trial design:

Multicenter, open label Phase Ib/IIa study consisting of 2 parts:

- A part 1 dose escalation phase lb to confirm the safety of IPH2201 as a single agent during 4 weeks and thereafter combined with ibrutinib during 52 weeks
- · A part 2 single-arm phase IIa assessment of IPH2201 combined with ibrutinib during 52 weeks

During the phase lb, a 3+3 design will be employed. Four doses are planned to be assessed if MTD is not previously reached:

Dose level 1: 1 mg/kg Dose level 2: 2 mg/kg Dose level 3: 4 mg/kg

Dose level 4: 10 mg/kg

[figure not shown]
Three patients will be entered at each dose level. If a Dose Limiting Toxicity (DLT) is encountered in the initial cohort at a given dose level, that cohort will be expanded to a total of 6 patients.

Release date: Edition number 12 August 2016 MOD-3783

**GED** version

MTD will be considered to have been exceeded if >1/6 patients experience a DLT at that same dose level. MTD will be sought at the previous dose level by enrolling 3 additional patients, unless this cohort has been previously expanded to 6. If less than 2 out of 6 patients develop a DLT at that level, it will be defined as the MTD.

Dose-escalation will be based on a review by the safety committee of the data from all patients of the *current* cohort, after they have completed first 2 cycles of single agent IPH2201.

Introduction of ibrutinib at a new dose level will be allowed by the safety committee after review of the data of all patients of the *previous* cohort, after they have completed 2 cycles of IPH2201 in combination with ibrutinib.

During the phase IIa, patients will receive IPH2201 in combination with ibrutinib from the first day of the phase IIa.

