### IPH2201 treatment delay:

 A delay of up to 2 weeks during phase Ib and 4 weeks during phase IIa in the treatment schedule is authorized in the absence of resolution to a grade 2 or lower of any grade ≥ 3 adverse events.

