### Part 1: phase lb

In the part 1, dose escalation phase Ib of the trial, 4 doses are planned to be assessed if MTD is not previously reached:

Dose level 1: 1 mg/kg Dose level 2: 2 mg/kg Dose level 3: 4 mg/kg Dose level 4: 10mg/kg

At each of the explored dose levels, a period of at least 7 days must be respected between the first IPH2201 administration of the first treated patient and the first IPH2201 administration of the following patients.

In the part 2, phase IIa of the clinical trial, the doses of IPH2201 will be selected by the safety committee.

Intra-patient dose escalation is not allowed.

In case of any grade ≥3 adverse event:

- Treatment will be temporarily suspended for one week
- Treatment will be resumed at the same dosage in case of resolution to a grade 2 or lower
- In the absence of resolution to a grade 2 or lower, the treatment suspension will be prolonged by 1 more week
- In the absence of resolution to a grade 2 or lower after a 2-week suspension, the patient will be taken off study
- In case of recurrence of a grade 3 related reaction after a temporary suspension, the same suspension will apply, but after resolution to a grade 2 or lower, treatment will be resumed at the lower dose level

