# 4.3.2 Patient Replacement Policy

In any case, if patients do not receive at least 1 administration of IPH2201.

In the two phases of the trial (Ib and IIa), in case of treatment discontinuation of IPH2201 due to disease progression before the end of 8 weeks of treatment.

Release date: Edition number

GED version

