# 9.2 SAFETY ASSESSMENTS

Subjects will be considered evaluable for safety if they have received any dose of the study drug. Toxicity assessments will be continuous during the Treatment period and the Clinical Follow-up periods.

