9.3 Adverse Events

Adverse events (AEs) will be coded using the Medical Dictionary for Regulatory Activities and will be graded according to the National Center Institute Common Terminology Criteria for AEs (NCI-CTCAE criteria [v4.0] [3]). Adverse events will be analyzed in terms of their type, incidence, severity and relationship to the study treatment. Related AEs are defined as events with a relationship to study treatment equal to 'possibly related', 'probably related', or 'definitively related' or with missing relationship.

Adverse events in this section will be tabulated if they are treatment-emergent (TE), see definition in Section 4.4. Partial dates will be handled according Section 4.5.

A summary table will present the frequency of patients with at least one:

- TEAE
- TEAE related to monalizumab or ibrutinib
- TEAE related to monalizumab
- TEAE related to ibrutinib
- TEAE causing monalizumab or ibrutinib discontinuation
- TEAE causing monalizumab discontinuation
- TEAE causing ibrutinib discontinuation
- TEAE causing dose delayed of monalizumab
- TEAE causing monalizumab infusion interrupted
- TEAE causing dose reduction of monalizumab at the lower dose level
- TEAE causing dose reduction of ibrutinib
- TEAE causing dose interruption of ibrutinib
- Grade 3 or worse TEAE
- Serious TEAE
- Monalizumab or ibrutinib related serious TEAE
- Monalizumab related serious TEAE
- Ibrutinib related serious TEAE
- Fatal TEAE
- Fatal TEAE related to monalizumab or ibrutinib

In addition, tabulations of the number of patients who experienced TEAEs as well as severity of the events will be presented by SOC and PT, by grade, by dose and overall. Patients will only be counted once for each preferred term. In case a patient experienced the same event more than once, the worst severity will be presented.

The following tabulations will be presented:

TPL Version: 02

[figure not shown]
- All TEAEs
- Monalizumab or ibrutinib related TEAEs
- Monalizumab related TEAEs
- Ibrutinib related TEAEs
- TEAE causing monalizumab or ibrutinib discontinuation
- TEAE causing monalizumab discontinuation
- TEAE causing ibrutinib discontinuation
- TEAE causing dose reduction of monalizumab at the lower dose level
- TEAE causing dose reduction of ibrutinib
- Grade 3 or worse TEAE
- Serious TEAEs
- Monalizumab or ibrutinib related Serious TEAEs
- Monalizumab related Serious TEAEs
- Ibrutinib related Serious TEAEs
- Fatal TEAE

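### Phase Ib: the 2-week off-study limit coincides with the delay-DLT threshold, so removal for certain persistent cytopenias need not be scored as a DLT

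*Protocol*

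**What the plan says.** **Suspension.** Protocol 3.3.1 (Part 1: phase Ib) suspends IPH2201 for one week after any grade ≥3 AE, and for one further week if the AE is still above grade 2. It then states: "In the absence of resolution to a grade 2 or lower after a 2-week suspension, the patient will be taken off study". The synopsis, under IPH2201 treatment delay, gives the same ceiling: "A delay of up to 2 weeks during phase Ib and 4 weeks during phase IIa in the treatment schedule is authorized".

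**DLT list.** Protocol 9.3 and the synopsis give the same five criteria. Four name toxicities:

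- any grade 3–4 non-hematologic toxicity;
- grade 4 neutropenia persisting at least 7 days once therapy is stopped, if the pre-treatment neutrophil count (ANC) was at least 1,000/µl;
- grade 4 thrombocytopenia;
- grade 3–4 thrombocytopenia with bleeding.

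The fifth is "Any dose delay due to AE for > 14 consecutive days". All five apply to the first 4 cycles (8 weeks).

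**Use of the count.** One DLT among the first three patients expands a cohort to six. The synopsis adds: "MTD will be considered to have been exceeded if >1/6 patients experience a DLT at that same dose level".

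**Who is counted.** Protocol 9.2 says: "Subjects will be considered evaluable for safety if they have received any dose of the study drug". After a first dose, 4.3.2 replaces a patient only "in case of treatment discontinuation of IPH2201 due to disease progression before the end of 8 weeks of treatment". SAP 9.1 tabulates DLT occurrence and type without adding a definition.

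**The concern.** The suspension rule stops at the day on which the delay criterion has not yet been met, and nothing in the list picks up the patient who is then removed. Read literally, the order of severity is inverted. A patient held for 15 days against the protocol and then re-dosed is a DLT. A patient removed as the protocol requires, because the AE never resolved, is not a DLT unless another criterion covers the event.

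The two limits coincide only in phase Ib. In phase IIa, where the same list defines unacceptable reactions, suspension may last 4 weeks and the delay criterion can be met.

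DLT occurrence is a phase Ib primary endpoint, and the expansion and MTD rules are counts. Two careful readers could score the same removed patient differently. The events are plausible here: exclusion criterion 4 bars only cytopenias that are not due to CLL marrow failure.

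**Working it through.** The plan states no operating characteristic for the 3+3 part, so there is no figure to reproduce. The check applies the written rules to each type of event.

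**Step 1: can an IPH2201 hold meet the delay criterion?** Maximum suspension under 3.3.1 is 7 + 7 = 14 days. The test 14 > 14 is false. The test 15 > 14 is true, but 3.3.1 has already removed the patient. Of the five criteria, none makes discontinuation for an AE a DLT; the neutropenia criterion mentions stopping therapy only to start its 7-day clock.

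**Step 2: which events does that leave out?** Grade ≥3 AE unresolved after exactly 14 days of IPH2201 hold, ibrutinib left aside:

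| Event | DLT at day 14? | Through |
|---|---|---|
| Non-hematologic, grade 3–4 | yes | criterion 1 |
| Neutropenia grade 4, pre-treatment ANC ≥1,000 | yes | criterion 2 |
| Thrombocytopenia grade 4 | yes | criterion 3 |
| Thrombocytopenia grade 3 with bleeding | yes | criterion 4 |
| Neutropenia grade 3 (ANC 500 to <1,000) | no | – |
| Thrombocytopenia grade 3 (50–74% fall), no bleeding | no | – |
| Anaemia grade 3 or 4 | no | – |

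Grade 4 neutropenia with pre-treatment ANC below 1,000 is also unscored, but Appendix IV calls such patients not evaluable for ANC toxicity, so I do not count it as part of the gap.

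**Step 3: does ibrutinib close the gap?** The delay criterion names no drug. Under 3.3.2, ibrutinib is held for grade 4 hematologic toxicity, or for grade ≥3 neutropenia with infection or fever, until grade 1 or baseline, with no 14-day ceiling. From week 4 to week 8 such a hold could exceed 14 days and meet the criterion. That can capture grade 4 anaemia and complicated grade 3 neutropenia. It cannot help in weeks 0 to 4, before ibrutinib starts, and uncomplicated grade 3 cytopenias do not require an ibrutinib hold.

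**Step 4: effect on the rule.** If the patient stays in the cohort count, leaving out one such event turns 1/3 (expand) into 0/3 (no expansion), or 2/6 (MTD exceeded) into 1/6 (not exceeded).

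**Step 5: timing.** Take week 0 as day 0 and count the hold from the planned dosing day. The 2-week limit falls on:

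- week-2 dose: day 14 + 14 = 28;
- week-4 dose: day 28 + 14 = 42;
- week-6 dose: day 42 + 14 = 56;
- week-8 dose: day 56 + 14 = 70.

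The DLT window ends at day 56. An AE that starts in cycle 4 and holds the week-8 dose therefore reaches the limit only after the window has closed.

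**Step 6: size.** The documents give no rate for these events. For illustration only, the chance of passing a dose level at DLT rate p is (1−p)³ + 3p(1−p)⁵. With an assumed 10% rate of recognised DLTs this is 0.906. If unscored events occur in a further 5%, 10% or 20% of patients and were counted, it becomes 0.814, 0.709 or 0.494. These figures assume that the literal reading is always applied and that the committee never intervenes. They show that the answer depends wholly on an unknown rate; they do not estimate the effect.

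**The case against.** The strongest reply is that the two limits are meant to fit together: up to 14 days is permitted, and anything longer is dose limiting. A patient unresolved at day 14 does not receive the dose, and on day 15 it is still being withheld because of the AE. No text says that the delay stops counting at removal. This reading is plausible and may be the intended one. It is not stated, so the scoring ambiguity stands.

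The second reply is safety committee discretion. Under 9.3 the committee may lower the dose at any time in phase Ib, may stop escalation before an MTD is reached, and selects the phase IIa dose on all safety, pharmacology and activity data. In addition, a patient removed after a held week-2 dose has not completed the two single-agent cycles that the escalation review requires. This limits the practical risk but does not settle the reported DLT count.

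Some stronger inferences are tempting but unsupported:

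- *Any unresolved hematologic AE escapes the definition.* Criteria 2 to 4 already cover several, and an ibrutinib hold may cover others from week 4.
- *The SAP confirms that discontinuation is not a delay.* SAP 9.3 lists "TEAE causing dose delayed of monalizumab" and "TEAE causing monalizumab discontinuation" separately, but these count consequences of AEs. One event can appear under both, and the list says nothing about DLT scoring.
- *The removed patient is certainly a non-DLT in the 3+3 denominator.* Protocol 9.2 defines evaluability for safety, and 4.3.2 rules out replacement for an AE. Neither document defines a DLT-evaluable set, so the denominator is an inference.

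**Conclusion.** The gap is real on the wording, and it is minor. It is limited to persistent grade 3 neutropenia, grade 3 thrombocytopenia without bleeding and grade 3 anaemia, plus grade 4 anaemia where no ibrutinib hold longer than 14 days in weeks 4 to 8 triggers the criterion. The conclusion rests on two assumptions: that the delay is taken to end when the patient is removed, and that the removed patient remains in the cohort count. Both fit the text, but neither is written down.

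A reader might go further and infer that a dose above the true MTD would be declared acceptable. The documents do not support that: they give no event rates, and the committee is not bound to act on the count alone. What is at stake is consistent scoring of a primary endpoint, and through it the reported DLT count and MTD.

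**What to change.** In protocol 9.3 and the synopsis, keep the delay criterion and add this clause: *or IPH2201 discontinuation because an AE with onset in the first 4 cycles has not resolved to grade ≤2 after the 2-week suspension*. Tying it to AE onset brings in the held week-8 dose.

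In SAP 9.1, tabulate this as a DLT type. If escalation decisions have already been made, show it as a separate row, so that the DLTs reported still match those the committee used.

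The cost is one clause in two places and one table row. No new data are needed: protocol 4.3.1 records the primary reason for withdrawal, and SAP 5.1 summarises reasons for discontinuation. The downside is that the DLT count may be slightly less favourable.
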